9.2.3 Interim Analysis

This trial is designed to enroll up to approximately 200 subjects, randomized to active or control, following an equal allocation to treatment arms. An interim analysis of the data is planned after 30 subjects (n=15 subjects per arm) to evaluate the relative effect. At the interim analysis, the sample size may be re-estimated to include additional subjects to attain adequate power up to a 200 total subjects. This will be conducted at an alpha level of 0.001 and thus the overall alpha level for the final test will be performed at $\alpha=0.047$ instead of $\alpha=0.05$. The sponsor also reserves the right to alter the final sample size if the assumptions of the death rates are not satisfied at this interim analysis.

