6. INTERIM ANALYSIS AND EARLY STOPPING GUIDELINES

6.1 Interim Analysis

This trial is designed to enroll up to approximately 200 subjects, randomized to active or control, following an equal allocation to treatment arms. An interim analysis of the data is planned after 30 subjects (approximately n=15 subjects per arm) to evaluate the relative treatment effect.

The interim analysis will be conducted on the primary and secondary endpoint data at an alpha level of 0.001 and thus the overall alpha level for the final test will be performed at approximately $\alpha=0.049$ instead of $\alpha=0.05$.

At the interim analysis, the sample size may be re-estimated to include additional subjects up to a total of 300 subjects to attain adequate power beyond the sample size of 200 originally calculated. This evaluation will be based on the methodology suggested by Gould et al. (Gould AL. Interim analyses for monitoring clinical trials that do not materially affect the type I error rate. Stat Med 1992; 11(1): 55-66) Let σ be the pooled rate of this study endpoint in the two arms, i.e. $\sigma=(p_{placebo}+p_{Ampion})/2$, where p is the incidence of the primary study endpoint in the respective groups. Let σ^* be the same value, but based on some assumed rates for these values from the beginning of the trial. Then the following sample size multiplier is determined:

$$f = [\sigma(1-\sigma)]/\sigma^*(1-\sigma^*)$$

If f is greater than 1, then the new sample size, n_1 , is determined as $f \times n$, where n is the original sample size (per group) of 100. If f is less than one, then the study will continue as originally envisioned.

The sponsor reserves the right to alter the final sample size if the assumptions of the rates of the primary endpoint are not satisfied at this interim analysis.

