6.2 Blinding Controls at Interim Analysis

The interim analysis will involve unblinded data. Only a small sequestered team will have access to the unblinded data and results. The data will not be transferred, or results viewed by any person involved in the day-to-day conduct of the clinical trial, including, but not limited to the blinded sponsor staff, Medical Monitor, and/or blinded CRO staff. These individuals will remain blinded to the results.

The unblinded team will be responsible for obtaining the required material for the analysis from the study's unblinded data manager (DM) for the clinical trial. The unblinded team will present

Statistical Analysis Plan (SAP) for Clinical Study AP-017

the results of the interim analysis to the sponsor in a blinded fashion (e.g., a simple recommendation to increase sample size or keep sample size as defined in the SAP without presenting the details surrounding the raw data, results, or efficacy conclusions).

All individuals on the sequestered team who are unblinded will be documented and archived by the sponsor.

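### SAP 6.1 lets the sponsor alter the final sample size outside the pooled-rate rule, with no direction, limits or stated data basis, and the final test does not adjust for a size that depends on the interim effect

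*SAP*

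**What the plan says.** **The rule.** SAP 6.1 plans one interim look: "An interim analysis of the data is planned after 30 subjects (approximately n=15 subjects per arm) to evaluate the relative treatment effect". It defines σ as the average of the two arms' event rates, σ* as the same quantity under the starting assumptions, and f = σ(1−σ)/[σ*(1−σ*)]. If f exceeds one, the size per group becomes f × 100, up to 300 in total. Otherwise: "If f is less than one, then the study will continue as originally envisioned".

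**The clause.** The next paragraph reads: "The sponsor reserves the right to alter the final sample size if the assumptions of the rates of the primary endpoint are not satisfied", with reference to this interim analysis. Protocol 9.2.3 has a counterpart with a different trigger, a failure of the assumed death rates: "The sponsor also reserves the right to alter the final sample size".

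**Blinding.** SAP 6.2 states: "The interim analysis will involve unblinded data". It adds that only a small sequestered team sees those data. The sponsor receives a blinded message, and the example given is a simple recommendation to increase or to keep the size.

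**Test and alpha.** The primary test in SAP 3.1 and Protocol 9.4.1 is an ordinary chi-square or Fisher's exact test. The only adjustment is for the interim look at 0.001, which leaves about 0.049 for the final test in the SAP and 0.047 in the protocol. The cap on re-estimation is 300 in SAP 6.1 and 200 in Protocol 4.1 and 9.2.3. The protocol contains no f rule.

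**The concern.** The f rule uses only the sum of the two event rates, so the resulting size carries almost no information about the treatment difference and the ordinary final test stays close to its level. The clause that follows is not tied to f. The f rule already covers a pooled rate that is too high (increase) or too low (continue at 200). What the clause adds is therefore either an override of the f<1 rule, including a possible decrease, or a response to something other than the pooled rate.

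The second possibility matters for type I error. The sample-size assumptions in SAP 2.4 are stated by arm (8% and 22%), the look is described as evaluating the relative effect, and the data are unblinded. If the final size came to depend on the observed arm difference, no combination, weighted or conditional-error test is planned to protect the level. A reader of the final report could not tell from the plan whether that had happened.

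**Working it through.** **Inputs.** Interim at 30 patients; planned total 200, 1:1; rates 8% and 22%; two-sided 5%; interim alpha 0.001; final alpha 0.049 (SAP) or 0.047 (protocol); cap 300 (SAP) or 200 (protocol). Sources: SAP 2.4 and 6.1, Protocol 4.1 and 9.2.3.

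**1. The plan's own figures.** Exact binomial enumeration of the unpooled z-test with 100 per arm, 8% against 22%, gives power 81.28%; the stated 81.3% is reproduced. The SAP's final alpha is 0.05 − 0.001 = 0.049. With total size fixed at 200 and correlation √(30/200) between the two looks, overall type I error is 4.97% at 0.049 and 4.77% at the protocol's 0.047.

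**2. What the f rule does.** σ* = (0.08 + 0.22)/2 = 0.15, so σ*(1−σ*) = 0.1275.
- Pooled rate 0.20: f = 0.16/0.1275 = 1.255, total about 251.
- Pooled rate 0.10: f = 0.09/0.1275 = 0.706, below one, total stays at 200.
- Both arms at 0.15: σ = 0.15 and f = 1. The arm-specific assumptions have failed completely, yet the rule changes nothing.

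The last line shows the gap: a failure of the arm-level assumptions that f cannot see could still fall within the clause.

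**3. Error with the f rule binding.** Exact binomial calculation, chi-square test at 0.049, floor 200, cap 300: 4.97% at a common rate of 15% and 4.95% at 22%. There is no material inflation.

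**4. Upper bound if the size depends on the arm difference.** Let z be the null interim statistic at 30 patients, N the final total, t = 30/N, and c the two-sided critical value at 0.049. The conditional probability of final rejection is

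Φ((√t·z − c)/√(1−t)) + Φ((−c − √t·z)/√(1−t)).

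For each z, take the N in the allowed range that maximises this, count interim rejection at 0.001, and integrate over the null distribution of z.

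| Allowed total size | Maximum type I error, final alpha 0.049 |
|---|---|
| fixed at 200 | 4.97% |
| 200 to 300 (SAP 6.1 limits) | 5.24% |
| 100 to 300 (assumed floor) | 5.97% |
| 60 to 300 (assumed floor) | 6.87% |
| 31 to 300 (assumed floor) | 9.62% |
| 30 to 300 (may stop at the interim) | 10.4% |

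At the protocol's 0.047 the bound is 5.74% for 100 to 300 and 9.26% for 31 to 300.

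**5. Dependence on the test.** Exact binomial calculations at common rates of 15% and 22% give 5.24% to 5.28% for the chi-square test within 200 to 300. With Fisher's exact test, the maximum is 3.5% to 3.7% within 200 to 300 and 5.1% to 5.7% within 32 to 300.

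**The case against.** A reader might infer that the sponsor can change the size at will after seeing results by arm, and that the true type I error is therefore 6% or even 10%. The documents do not support that.

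- **The right is conditional.** Both versions require that the rate assumptions are not satisfied. The condition is undefined, but it exists.
- **The holder of the right is blinded.** Under SAP 6.2 the sponsor gets a recommendation without results or efficacy conclusions. All the inflation figures need the choice of size to follow the observed difference.
- **The rates need not be arm-specific.** The clause comes directly after a rule that compares a pooled rate with its assumed value, so a pooled reading is equally possible. A blinded sponsor could apply it from the overall event count.
- **The low floors are not in the plan.** The only re-estimation range in SAP 6.1 is 200 to 300, where the bound is about 0.3 percentage points above the fixed-size value (5.24 − 4.97 = 0.27).
- **Fisher's exact test is allowed**, and it is conservative here.

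All five points stand as limits on the size of the problem. They do not remove it. The blinding of the sponsor does not by itself protect the level: if the unblinded team's recommendation reflects the arm difference, a sponsor acting on it makes the size depend on that difference without ever seeing it. A sponsor who is truly blinded cannot judge whether arm-level assumptions failed, so the clause has no legitimate arm-level use. A decrease, which the word alter permits, lies outside both the f rule and the example recommendation in SAP 6.2.

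**Conclusion.** The clause is an unbounded exception next to a prespecified rule. It conflicts with the f<1 provision and is not tied to the blinding arrangements in SAP 6.2. If it is used on the blinded pooled rate only, type I error stays at about 5%. If the size came to depend on the interim difference, the chi-square or z-test bound is about 5.2% within the SAP's 200 to 300, about 6% with an assumed floor of 100, and about 10% if the trial could stop at or just after 30.

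These are maxima under the choice of size most favourable to rejection, not estimates of what will happen, and they rest on normal theory and a final alpha of 0.049. The documents do not show that the sponsor would act on arm-level data. The defect is that the plan does not rule it out, directly or through the recommendation, and that the final test offers no protection if it happens. That justifies a change before the interim analysis.

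**What to change.** 1. Delete the clause in SAP 6.1 and its counterpart in Protocol 9.2.3. Alternatively, restrict it to the f rule computed on the blinded pooled rate, with a floor of 200 and one stated cap.
2. Put the same f rule in Protocol 9.2.3. Deleting the clause there without this would leave re-estimation in the protocol with no method.
3. Reconcile the documents on the cap (200 against 300), the final alpha (0.047 against 0.049) and the trigger (death rates against the composite primary endpoint).
4. State that any other change of size is made by protocol amendment, by staff without access to arm-level data.

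The cost is a short amendment to both documents and some loss of sponsor flexibility. No additional data are needed.

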6.2 Blinding Controls at Interim Analysis

The interim analysis will involve unblinded data. Only a small sequestered team will have access to the unblinded data and results. The data will not be transferred, or results viewed by any person involved in the day-to-day conduct of the clinical trial, including, but not limited to the blinded sponsor staff, Medical Monitor, and/or blinded CRO staff. These individuals will remain blinded to the results.

The unblinded team will be responsible for obtaining the required material for the analysis from the study's unblinded data manager (DM) for the clinical trial. The unblinded team will present

Statistical Analysis Plan (SAP) for Clinical Study AP-017

the results of the interim analysis to the sponsor in a blinded fashion (e.g., a simple recommendation to increase sample size or keep sample size as defined in the SAP without presenting the details surrounding the raw data, results, or efficacy conclusions).

All individuals on the sequestered team who are unblinded will be documented and archived by the sponsor.

6.3 Stopping Rules

The study may be stopped upon recommendation by the safety monitoring committee.

7. DATA HANDLING AND ELECTRONIC TRANSFER OF DATA

See Data Management Plan (DMP).

7.1 Handling of Missing and Incomplete Data

Incomplete adverse event and concomitant medication dates will be imputed as described in Section 11. If imputed dates are used, then they will be identified as such in the final study report. If an AE start date is missing or partially missing and no additional information is available from the site in order to establish whether the event started before or after the dose of study drug, the event will be considered to have started after dose. Partially missing dates where the month and year is prior to Day 0 will not be classified as post dose.

For the primary effectiveness endpoint analysis, need for mechanical ventilation or death prior to Day 28, a sensitivity analysis will be performed for all patients that have been discharged from the hospital, cannot be reached via telephone contact, and their death status is not known. The sensitivity analysis will be performed where missing mechanical ventilation or death status at Day 28 will be replaced as having died.

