9.5 Missing and Spurious Data

All data collected under this study protocol will be included in the assessment of patient safety. Missing or incomplete AE data will assume greatest relationship to study drug and/or severity.

For the effectiveness endpoint analysis of all-cause mortality at Day 28 and 60 a sensitivity analysis will be performed for all participants that have been discharged from the hospital, cannot be reached via telephone contact, and their death status is not known. The sensitivity analysis will be performed where missing mortality status at Day 28 and 60 will be replaced as having died.

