2.4 Sample Size

The trial is designed to enroll up to approximately 200 patients across two treatment arms (active or control), with 100 subjects per arm, randomized 1:1 using a random allocation sequence stratified by COVID-19 disease severity (severe or critical). An interim analysis of the data is planned after 30 subjects (approximately n=15 subjects per arm) to evaluate the relative effect. At the interim analysis, the sample size may be re-estimated to determine the additional number of patients required for adequate power to meet the chosen effect size for the primary endpoint.

The number of participants is selected based on the effects observed for the primary endpoint, prevention of need for mechanical ventilation or death prior to day 28. A study recently reported in Lancet Respiratory Medicine with 243 hospitalized patients receiving the placebo for COVID-19 found 22% did not achieve day 28 ventilation-free survival (Lancet Respir Med 2021; [https://doi.org/10.1016/S2213-2600\(21\)00494-X](https://doi.org/10.1016/S2213-2600(21)00494-X)). In the AP-014 study, a lower rate (8%) was observed for subjects receiving inhaled Ampion. Assuming the same proportions (8% for Ampion and 22% for control) by Day 28, with 100 subjects per group, a two-sided 5% significance level, and using a z-test with unpooled variances, then under binomial enumeration the power to detect this difference is about 81.3%.

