3. STUDY ENDPOINTS AND ANALYSES

Statistical Analysis Plan (SAP) for Clinical Study AP-017

3.1 Primary Endpoint:

The primary endpoint assesses the effect of Ampion compared to placebo on prevention of need for mechanical ventilation or death prior to day 28. This is measured as the occurrence of mechanical ventilation or death by Day 28.

Let π_A and π_S represent the rate of this outcome for Ampion and control during the first 28 days after randomization. Then it is desired to demonstrate that the mechanical ventilation and death rate for Ampion is different than the corresponding rate for the control. Formally, this is presented as:

$$H_0: \pi_A = \pi_S \text{ versus } H_A: \pi_A \neq \pi_S$$

This will be tested utilizing the appropriate chi-square test or Fisher's exact test utilizing PROC FREQ with the EXACT option, if necessary.

Also, the median time to mechanical ventilation or death will be tested for difference between the two groups via the log-rank test. The test will be performed using PROC LIFETEST. The time to event distributions in each group will be estimated using the method of Kaplan and Meier.

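### The only stated imputation for the primary composite counts missing patients as died in both arms alike: it is not guaranteed conservative and never tests the allocation that could overturn a positive result

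*SAP*

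**What the plan says.** SAP 3.1 tests the composite by comparing proportions: "This will be tested utilizing the appropriate chi-square test", or Fisher's exact test if needed. SAP 5.1.2 puts every randomized patient in the efficacy population. Neither section says what the test does with a patient whose Day 28 status is unknown. SAP 3.1 adds a log-rank test with Kaplan-Meier curves for the same outcome, but gives no censoring rule.

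The one imputation rule is in SAP 7.1. It is a sensitivity analysis restricted to patients who meet three conditions together: discharged, not reachable by telephone, and death status unknown. For them, "missing mechanical ventilation or death status at Day 28 will be replaced as having died". The arms are treated identically.

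Protocol 9.5 has the parallel rule, but for all-cause mortality and not for the composite: "missing mortality status at Day 28 and 60 will be replaced as having died". SAP section 9 explains the difference in part, because the primary endpoint was changed from mortality alone to the composite.

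Neither document gives an expected loss rate, an analysis that varies the assumption by arm, a tipping-point analysis or multiple imputation.

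**The concern.** Loss of Day 28 status is foreseeable. Treatment lasts five days, later contact is mostly by telephone (Protocol 5.1), and in the Protocol's schedule (1.2) the next visit after Day 7 is Day 28.

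A sensitivity analysis on a positive result should ask how unfavourable to the new treatment the missing outcomes would have to be before the conclusion fails. Giving both arms the same extreme value does not ask that. It adds events in proportion to each arm's losses. With balanced losses it adds about the same number to each side and leaves most of the difference standing. With more losses on placebo it widens the difference. In neither case does it examine missing Ampion patients having events while missing placebo patients do not.

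What is at stake is the credibility of the robustness statement. At 100 patients per arm a few unknown outcomes can decide significance, and the planned check could support a result that another possible allocation of the same missing patients would overturn.

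**Working it through.** **Inputs from the documents.** Rates and group size, from SAP 2.4: "Assuming the same proportions (8% for Ampion and 22% for control) by Day 28, with 100 subjects per group". The planning test in that section is a two-sided z-test at the 5% level that uses each arm's own variance. The final alpha after the interim look is approximately 0.049 in SAP 6.1 and 0.047 in Protocol 9.2.3.

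**Inputs assumed.** The numbers missing and the observed event counts. The complete-case starting point is also an assumption, because no rule for the primary test is stated.

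**Step 1: the plan's own figure.** SAP 2.4 says "under binomial enumeration the power to detect this difference is about 81.3" per cent. Sum Bin(x; 100, 0.08) × Bin(y; 100, 0.22) over all x and y from 0 to 100 for which |x − y|/100 ÷ √{[p₁(1 − p₁) + p₂(1 − p₂)]/100} ≥ 1.96, with p₁ = x/100 and p₂ = y/100. The total is 0.8128. The stated power reproduces, with complete outcome data in all 200 patients.

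**Step 2: the test.** Uncorrected Pearson chi-square for a events in n₁ Ampion patients and b in n₂ placebo patients, with N = n₁ + n₂ and e = a + b:

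X² = N[a(n₂ − b) − b(n₁ − a)]² ÷ [n₁ n₂ e (N − e)], on 1 degree of freedom.

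**Step 3: equal loss, 4 missing per arm, 8/96 against 20/96 observed.**

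- Complete case: 192 × (8×76 − 20×88)² ÷ (96×96×28×164) = 192 × 1152² ÷ 42,319,872 = 6.02, p = 0.014.
- Planned rule, 12/100 against 24/100: 200 × 1200² ÷ (100×100×36×164) = 4.88, p = 0.027.
- Ampion missing = event, placebo missing = no event, 12/100 against 20/100: 200 × 800² ÷ (100×100×32×168) = 2.38, p = 0.12.

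The intermediate cells, holding placebo at 20 events, show where the result tips:

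- 2 of the 4 missing Ampion patients with events, 10 against 20: 200 × 1000² ÷ (100×100×30×170) = 3.92, p = 0.0477.
- 3 of the 4, 11 against 20: 200 × 900² ÷ (100×100×31×169) = 3.09, p = 0.079.

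The 10-against-20 cell is significant at the SAP's 0.049 and not at the Protocol's 0.047, so the table needs one agreed alpha.

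**Step 4: more loss on placebo, 1 Ampion and 5 placebo missing, 9/99 against 17/95 observed.**

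- Complete case: 194 × (9×78 − 17×90)² ÷ (99×95×26×168) = 194 × 828² ÷ 41,081,040 = 3.24, p = 0.072.
- Planned rule, 10/100 against 22/100: 200 × 1200² ÷ (100×100×32×168) = 5.36, p = 0.021. This is below both stated alphas.

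**Step 5: more loss on Ampion, 8 Ampion and 2 placebo missing, 8/92 against 22/98 observed.**

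- Complete case: 190 × (8×76 − 22×84)² ÷ (92×98×30×160) = 190 × 1240² ÷ 43,276,800 = 6.75, p = 0.009.
- Planned rule, 16/100 against 24/100: 200 × 800² ÷ (100×100×40×160) = 2.00, p = 0.157. Here the rule is severe on Ampion.

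**Step 6: average behaviour of the imputed analysis.** Assume patients who would be event-free are lost at rate l and imputed as died, so the analysed rate is p + (1 − p)l. With the same true p = 15% in both arms, 100 per arm and chi-square at 0.05, exact enumeration gives these rejection rates:

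| Loss, Ampion / placebo | Rejection rate |
|---|---|
| 0% / 0% | 5.1% |
| 5% / 5% | 5.1% |
| 2% / 6% | 9.7% |
| 2% / 10% | 22.7% |

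At the planned 8% against 22%, equal loss of 5%, 10% and 15% lowers the power of the imputed analysis from 81% to 68%, 56% and 47%. The direction of the bias therefore depends on the balance of losses.

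**The case against.** Several points on the other side are sound.

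- **The rule is often conservative.** Steps 3, 5 and 6 show it raising p or losing power when losses are equal or heavier on Ampion. A reader might infer that it is anti-conservative in general; the arithmetic does not support that.
- **The primary test does not move.** A reader might infer from Step 4 that the rule can turn a failed trial into a positive one. SAP 7.1 calls it a sensitivity analysis, and nothing lets it replace the test in SAP 3.1.
- **It does not apply to all missing patients.** It covers only discharged, unreachable patients with unknown death status. This narrows the rule but widens the gap: in-hospital withdrawals, and patients known alive with unknown ventilation status, have no stated rule.
- **It is not the only other look at the outcome.** The log-rank analysis can use partial follow-up through censoring. With no censoring rule stated, however, it does not show what happens when the missing outcomes are unfavourable to Ampion.
- **Unbalanced loss is not predicted.** The trial is double-blind with a matching placebo, and the documents give no reason to expect five times as many losses on placebo. That limits the weight of Step 4. Step 3 does not need imbalance.
- **The Ampion-adverse corner is itself extreme.** It is, which is why it should be one cell in a table and not the verdict. Whether death is an unlikely outcome for a discharged patient is clinical inference that the documents do not quantify, and the point does not rest on it.

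**Conclusion.** The concern holds in a limited form. The one stated imputation for the primary composite is not a worst case for Ampion. Depending on the balance of losses it can weaken or strengthen the apparent effect, and it cannot show whether a positive result would survive unfavourable missing outcomes. With 4 missing per arm, the planned check reports p = 0.027 while an allocation it never examines gives p = 0.12. With 1 and 5 missing, the sensitivity p-value falls from 0.072 to 0.021 with the primary test unchanged.

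These sizes rest on assumed losses and event counts, a complete-case start, 100 per arm and the uncorrected chi-square test. If very few patients are lost, the issue may have no practical effect. The related gap, that the primary test has no rule for missing status, does not depend on those assumptions.

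**What to change.** Amend SAP 7.1, and Protocol 9.5 to match, before the study data are unblinded:

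1. Use the mortality and intubation/extubation dates already scheduled at Day 60 (Protocol 1.2 and 5.2, SAP section 12) to establish Day 28 status wherever possible. The list in Protocol 5.1.5 omits the intubation dates and should be brought into line.
2. State how the primary ITT chi-square or Fisher test treats patients whose status is still missing, including in-hospital withdrawals and patients known alive with unknown ventilation status.
3. Replace the single imputation with a table that varies the number of events among missing patients separately by arm. Keep all missing = event as one cell, include Ampion missing = event with placebo missing = no event, and report where p crosses the final alpha. Settle first whether that alpha is 0.047 or 0.049.
4. Word Protocol 9.5 for the composite.

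The cost is one table and a paragraph of SAP text, plus the matching protocol wording. No new data are needed. The price to the sponsor is that a positive result may look less robust than under the present rule.
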